### **13.3. Assessment of Causality**

The relationship of each adverse event to administration of the study drug(s) will be assessed by the Investigator after careful consideration of all relevant factors such as (but not limited to) the underlying study indication, co-existing disease, concomitant medication, relevant history, pattern of the adverse event, temporal relationship to receipt of the study medication(s) and de-challenge or re-challenge.

Study drug or study treatment refers to intravenously-administered doxorubicin and intravenously-administered TTI-621. The assessment of relationship to study drug or study treatment will be done for

each drug separately. If the Investigator feels such a distinction cannot be made, the assessment will be based on the combination of the two drugs.

The assessment of causality is based on the question of whether there was a reasonable causal relationship to the study drug in question according to the following guidelines:

**RELATED** (possible, probably or definitely related): there is a reasonable possibility that the study treatment caused the event; one or more of the following criteria apply:

- The event follows a reasonable temporal sequence from administration of study treatment
- The event could not be reasonably attributed to the known characteristics of the patient's clinical state, environment or toxic factors or other modes of therapy administered to the patient
- The event follows a known pattern of response to study treatment
- The event disappears or decreases on cessation or reduction in dose of the study treatment. In some situations, an AE will not disappear or decrease in intensity upon discontinuation of the study treatment despite other clear indications of relatedness

**UNRELATED** (unlikely related or definitely not related): There is no reasonable possibility that the study treatment caused the event; one or more of the following criteria apply:

- The event does not follow a reasonable temporal sequence from administration of study treatment
- The event could be reasonably attributed to known characteristics of the patient's clinical state, concurrent illness, environment or toxic factor or other therapies administered to the patient
- The event does not follow a known pattern of response to study treatment

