### 9.3 Adverse Events

Adverse events (AEs) will be documented on the AE eCRF and monitored continuously throughout the study. Adverse events will be coded using the Medical Dictionary for Regulatory Activities (MedDRA), latest version, associating lower-level terms with PT and SOC by the primary hierarchy.

Treatment Emergent Adverse Events (TEAEs) are those events with onset date occurring during the on-treatment period. The tables will display counts and percentages of patients who reported at least one TEAE in each SOC represented in the AE data. Within each SOC, the tables will display the counts and percentages of patients reporting at least one TEAE, as designated by the PT.

The severity of adverse events will be graded using the NCI Common Toxicity Criteria for Adverse Events (CTCAE version 5.0). The intensity is assigned a grade of 1 through 5 using the following CTCAE guidelines: Grade 1 – Mild; Grade 2 – Moderate; Grade 3 – Severe; Grade 4 – Life-threatening; Grade 5 – Death.

The causality of AE are reported as either related to study drug or not related to study drug for each study drug. Related AEs are those related to any study drug (i.e., at least one of the study drugs).

Pfizer Inc. / Protocol: TTI-621-03/C4961003  
IQVIA Biotech (Confidential) Project # YXA42460

If a patient has multiple occurrences of an adverse event, the strongest level of relationship to study drug(s) and the worst toxicity grade a patient experiences for a given AE will be used in these tables. No imputation will be performed for missing toxicity grade or causality data.

AEs that have missing onset dates will be considered as TEAE unless the stop date is known to be prior to the first administration of the study medication. If the AE onset date is partial, the date will be correlated as far as possible with the date of first dose of study medication. AE will be assumed to be TEAE, unless there is clear evidence (through comparison of partial dates) to suggest that the adverse event started prior to the first dose of study medication. Detailed imputation rules can be found in section 6.3. If patients died during the study and experienced AEs at the time of death, the AEs that lead to death will use death date as the AE end date; otherwise, AEs that do not lead to death will be reported as ongoing.

Adverse Events of Special Interest (AESI) include the following:

- Thrombocytopenia: Haematopoietic thrombocytopenia – SMQ Broad

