- Anemia: Haematopoietic erythropenia – SMQ broad
- Hemorrhage: Haemorrhage terms (excl. laboratory terms) – SMQ narrow
- Infusion related reactions (PT of Infusion-related reaction as recorded on the Adverse Event CRF)

The following TEAE summary tables will be produced by treatment group as described in Section 6.1:

- a. An overall summary of safety will summarize the numbers (and percentages) of patients with the following:
  - TEAEs (separately for combination period and monotherapy period, and overall), where combination period is defined as from the date of first study treatment to the date of last doxorubicin + 21 days
  - Grade  $\geq 3$  TEAEs (separately for combination period and monotherapy period, and overall)
  - Treatment-related TEAEs (separately for combination period and monotherapy period, and overall)
  - Treatment-related grade  $\geq 3$  TEAEs (separately for combination period and monotherapy period, and overall)
  - Serious TEAEs
  - Treatment-related Serious TEAEs
  - TEAEs leading to dose reduction (of PF-07901800 and doxorubicin, separately)
  - TEAEs leading to drug interruption (of PF-07901800 and doxorubicin, separately)

Pfizer Inc. / Protocol: TTI-621-03/C4961003  
IQVIA Biotech (Confidential) Project # YXA42460

- TEAEs leading to permanently discontinued study drug (PF-07901800, doxorubicin, and both)
- Treatment related TEAEs leading to permanent discontinuation of PF-07901800
- Treatment-related TEAEs leading to permanent discontinuation of doxorubicin
- Treatment-related TEAEs leading to permanent discontinuation of both drugs
- TEAEs leading to death
- Treatment-related TEAEs leading to death
- At least one TEAE of special interest: Thrombocytopenia SMQ (broad)
- At least one TEAE of special interest: Anemia SMQ (broad)
- At least one TEAE of special interest: Hemorrhage SMQ (narrow)
- At least one TEAE of special interest: Infusion related reactions

b. Separate summaries of TEAEs by SOC and PT, as follows:

- TEAEs by maximum severity (separately for combination period and monotherapy period, and overall)
- Treatment-related TEAEs (separately for combination period and monotherapy period, and overall)
- DLT
- Serious TEAEs
- Treatment-related Serious TEAEs
- TEAEs leading to dose reduction (of PF-07901800 and doxorubicin separately)
- TEAEs leading to drug interruptions (of PF-07901800 and doxorubicin separately)
- TEAEs leading to permanent discontinuation (of PF-07901800 and doxorubicin separately, and both)

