- Treatment-related TEAEs leading to permanent discontinuation of (of PF-07901800 and doxorubicin separately, and both)
- TEAEs leading to death
- Treatment-related TEAEs leading to death

c. Separate summaries of TEAEs by PT, as follows:

- Most common TEAEs (Any grade and Grade  $\geq$  3)  
Most common Treatment-related TEAEs (Any grade and Grade  $\geq$  3)

d. Summary of TEAEs (any grade and Grade  $\geq$  3) of special interest will be summarized by SMQ and PT, as applicable:

- Thrombocytopenia (broad)
- Anemia (broad)

Pfizer Inc. / Protocol: TTI-621-03/C4961003

IQVIA Biotech (Confidential) Project # YXA42460

- Hemorrhage (narrow)
- e. Summary of infusion related reactions (any grade and Grade  $\geq 3$ ) by SOC and PT

The following AE listings will be produced, sorted by dose cohort, patient, and timing, with relevant information:

- All AEs
- All DLTs
- AEs leading to death
- COVID-19 related AEs

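### For a recurring adverse event, SAP 9.3 takes the strongest causality and the worst grade without tying them to one occurrence, so treatment-related Grade ≥3 tables can count events that did not happen

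*SAP*

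**What the plan says.** SAP 9.3 sets a collapsing rule for its summary tables. Where the same event occurs more than once in one person, the instruction is that "the strongest level of relationship to study drug(s) and the worst toxicity grade a patient experiences for a given AE will be used". The rule names two maxima for a given term and does not link them.

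The causality scale is binary: "The causality of AE are reported as either related to study drug or not related to study drug for each study drug". An event counts as related if it is attributed to at least one of the two drugs. The strongest level is therefore simply related whenever any single occurrence was so judged.

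Two of the planned outputs cross relationship with grade:

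- The overall safety summary (SAP 9.3, item a) has a row for treatment-related Grade ≥3 events, presented "separately for combination period and monotherapy period, and overall".
- The by-preferred-term summaries (SAP 9.3, item c) include "Most common Treatment-related TEAEs (Any grade and Grade" ≥3.

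Protocol 12.3.1 lists incidence tables by maximum severity and incidence tables of related events as separate items. It gives no rule for combining the two attributes.

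**The concern.** If the two maxima come from different episodes, the patient-level record in the table describes an event that nobody observed. A mild related episode supplies the label, and a severe unrelated episode of the same term supplies the grade.

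Safety is a primary endpoint in dose escalation, and the safety of the selected doses is a primary objective in the expansion (SAP 2.1 and 3.1). Repeated episodes of one term are realistic here. TTI-621 is infused twice per cycle, Protocol 3.8.1 describes transient platelet falls after infusion, and Protocol 9.5 plans for second occurrences of thrombocytopenia. At stake is whether the treatment-related Grade ≥3 percentages reported for each cohort mean what their title says. The cohorts are small enough for one patient to be visible.

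**Working it through.** The documents give no figure on this point, so there is none to reproduce. The check is on the rule itself.

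**Step 1: what each derivation returns.** Take the occurrences of one term in one patient and ask whether the patient counts as treatment-related Grade ≥3.

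| Occurrences of one term | SAP 9.3 as worded (two separate maxima) | At least one occurrence both related and Grade ≥3 | Related occurrences first, then worst grade |
|---|---|---|---|
| related G1; unrelated G3 | yes | no | no |
| related G3; unrelated G1 | yes | yes | yes |
| related G1; related G3 | yes | yes | yes |
| single related G2 | no | no | no |
| single unrelated G4 | no | no | no |

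Only the first pattern separates the derivations. The last two columns always agree.

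**Step 2: direction.** Any occurrence that is both related and Grade ≥3 satisfies both maxima, so every patient who should be counted is counted. The rule can add patients but cannot remove them. The patients added are those with at least one related occurrence, at least one Grade ≥3 occurrence, and none that is both.

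**Step 3: which outputs move.**

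- *By preferred term (item c):* the extra patient appears under that term.
- *Overall row (item a):* the patient is added only if no other event, under any term, is truly related and Grade ≥3. Otherwise the patient is already in the count and adds nothing.
- *Not affected:* all-causality maximum-severity tables (grade only), any-grade related tables (relationship only), DLTs (their own Cycle 1 event definition, SAP 9.2), special-interest tables (no relatedness filter, SAP 9.3 items d and e) and laboratory shift tables (no attribution, SAP 9.5).

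**Step 4: weight of one patient.** Cohort sizes are from SAP 4.3.2: 31 planned for Cohort A, 18 for Cohort B and 13 for Cohort C.

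- 1/31 = 3.2 percentage points
- 1/18 = 5.6 percentage points
- 1/13 = 7.7 percentage points

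**Step 5: frequency, illustration only.** The documents say nothing about how often causality differs between episodes of one term. Assume a patient with exactly two occurrences, each related with probability r and Grade ≥3 with probability g, all independent. The misclassified pattern then has probability 2·r(1−r)·g(1−g).

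- r = 0.2 or 0.8, g = 0.1: 2 × 0.16 × 0.09 = 0.029
- r = 0.5, g = 0.4: 2 × 0.25 × 0.24 = 0.12
- r = 0.9, g = 0.4: 2 × 0.09 × 0.24 = 0.043

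Over r from 0.2 to 0.8 and g from 0.1 to 0.4, this gives about 3% to 12% of patients who have two occurrences of the term. It is not a share of the cohort. If an investigator tends to attribute repeat episodes of one term alike, the share would be lower.

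**The case against.** The strongest reply is that the sentence need not be read as building one composite record. The worst grade could govern only the severity tables and the strongest relationship only the relatedness tables, which matches the separate lists in Protocol 12.3.1 and SAP 9.3 item b. The overall row can also be read naturally as patients with at least one event having both attributes. These are sensible intentions, but the SAP states neither. It says that both maxima are used in the tables, and some of those tables cross the two. A programmer following the text could produce the overcount.

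Other parts of the reply stand. The tables are descriptive (Protocol 12.4), so no test or decision rule changes. The listing of all adverse events lets a reader see the individual episodes.

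Several stronger readings are tempting, and the documents do not support them:

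- *That discordant episodes are common.* Recurrence is realistic, but nothing in the documents reports causality differing between episodes of one term.
- *That counting attribution to either drug as related widens the error.* The error needs discordance. In Step 5 the probability falls from 0.12 to 0.043 as r rises from 0.5 to 0.9, so a broader definition of related can reduce it.
- *That these tables are a main input to dose choice.* Escalation rests mainly on DLTs (Protocol 5.1 and 5.4). SAP 4.3.2 attributes the closure of Cohort B to Grade 3 or 4 thrombocytopenia on Day 8, without reference to a treatment-related rate.
- *That separate tables of PF-07901800-related events are needed to cure the defect.* They are a different preference. Protocol 13.3 says "The assessment of relationship to study drug or study treatment will be done for" each drug separately, but falls back on the combination when the investigator cannot distinguish the drugs, so such tables may not be clean.

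**Conclusion.** The point holds as a defect of wording with a known direction and unknown frequency. As written, SAP 9.3 permits a treatment-related Grade ≥3 count with no matching occurrence, chiefly in the by-preferred-term table and conditionally in the overall row. The bias is upward or zero.

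The supportable size is per patient: 3.2, 5.6 or 7.7 points in cohorts of 31, 18 or 13. These figures take the cohort sizes in SAP 4.3.2 as denominators. For the overall row they also assume that the patient is not already counted through another event. A total overstatement per cohort cannot be stated, because the number of affected patients is not in the documents. The concern is minor: it affects the accuracy of a few descriptive safety figures, not the trial's design or its decision rules.

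**What to change.** Replace the collapsing sentence in SAP 9.3 with:

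*For tables of treatment-related TEAEs by grade, select related occurrences within the tabulated period first, then use the worst grade among them; for all-causality tables, use the worst grade regardless of relationship.*

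The words on the tabulated period also settle something the SAP leaves open. The overall row is split into combination and monotherapy periods, but the text does not say whether the maxima are taken within each period or across both.

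The cost is one SAP sentence and the order of a filter in the adverse-event program. No new data are needed. It should be done before database lock.

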#### 3.5.2.1.2. Safety

Not unexpected in this patient population, 223/235 subjects (95%) experienced at least one treatment-emergent adverse event. Treatment-emergent adverse events reported for  $\geq 20\%$  of subjects were infusion-related reaction (106 subjects, 45%), fatigue (82 subjects, 35%), chills (58 subjects, 25%), pyrexia (53 subjects, 23%), diarrhea (50 subjects, 21%), nausea (50 subjects, 21%) and anemia (49 subjects, 21%). The incidence of treatment-emergent adverse events was generally similar across disease cohorts, although a higher incidence of anemia was reported in the AML cohort compared with the other disease cohorts and the overall study population.

The most frequently-reported treatment-related adverse events of any grade, summarized in [Table 1](#), were infusion-related reaction (103 subjects, 44%), chills (49 subjects, 21%), platelet count decreased (37 subjects, 16%), fatigue (36 subjects, 15%), thrombocytopenia (34 subjects, 14%), anemia (30 subjects, 13%), pyrexia (26 subjects, 11%), nausea (25 subjects (11%), diarrhea (22 subjects, 9%), headache (18 subjects, 8%), vomiting (16 subjects, 7%) and hypotension (13 subjects, 6%). The incidence of treatment-related adverse events was generally similar across disease cohorts, although the incidence of treatment-related anemia was higher in the AML and HL cohorts compared with other disease cohorts and the overall study population.

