#### 3.8.1. Expected Risks of TTI-621

In clinical trials to date enrolling almost 300 patients with a variety of oncologic indications across a range of TTI-621 dose levels primarily administered by intravenous infusion weekly until progression, TTI-621 has generally been safe and well-tolerated. In TTI-621-01, in which TTI-621 was administered intravenously on a weekly schedule in patients with various relapsed/refractory hematologic malignancies and select solid tumors, the most frequent treatment-related adverse event was infusion-related reaction in 44% of patients. The majority of infusion-related reactions were mild-to-moderate, with only 3% of patients experiencing infusion-related reactions Grade  $\geq 3$ . The infusion-related reactions were reported across all dose cohorts and occurred despite premedication with an anti-histamine and acetaminophen. This study incorporates a steroid into the prophylaxis regimen, which may be reduced or eliminated at the discretion of the Investigator in patients who do not experience infusion-related reaction.

The most frequent Grade  $\geq 3$  treatment-related adverse event was acute but reversible thrombocytopenia which occurred in 22% of patients and was not impacted by dose level. The transient decreases in platelet counts occurred in the 24 hours following infusion in the majority of subjects following intravenous exposure to TTI-621, consistent with augmented systemic phagocytic clearance of platelets. In the majority of cases, platelet counts returned to baseline levels within 1 week, enabling continued weekly dosing. No increased risk of bleeding or other clinical sequelae were observed. More detailed information about the known and expected risks and reasonably expected adverse events of TTI-621 may be found in the TTI-621 Investigator Brochure, which is the SRSD for this study.

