**Table 11. Definition of Infusion-Related Reaction by CTCAE Grade**

CTCAE Grade	Definition
Grade 1 IRR	Mild transient reaction; infusion interruption not indicated; intervention not indicated
Grade 2 IRR	Therapy or infusion interruption indicated but responds promptly to symptomatic treatment (e.g., anti-histamines, NSAIDS, narcotics, IV fluids); prophylactic medications indicated for $\leq$ 24 hours
Grade 3 IRR	Prolonged (i.e., not rapidly responsive to symptomatic medication, brief interruption of infusion, or both); recurrence of symptoms following initial improvement; hospitalization indicated for clinical sequelae
Grade 4 IRR	Life-threatening consequences; urgent intervention indicated

Note: An acute infusion reaction may occur with an agent that causes cytokine release (e.g., monoclonal antibodies or other biological agents). Signs and symptoms usually develop during or shortly after drug infusion and generally resolve completely within 24 hours of completion of infusion. Signs/symptoms may include: allergic reaction/hypersensitivity (including drug fever); arthralgia (joint pain); bronchospasm; cough; dizziness; dyspnea (shortness of breath); fatigue (asthenia, lethargy, malaise); headache; hypertension; hypotension; myalgia (muscle pain); nausea; pruritis/itching; rash/desquamation; rigors/chills; sweating (diaphoresis); tachycardia; tumor pain (onset or exacerbation of tumor pain due to treatment); urticaria (hives, welts, wheals); vomiting.

As described in [Section 5.2.1](#), prophylaxis is required prior to infusion of TTI-621. Patients will be closely monitored for signs and symptoms of hypersensitivity or allergic reactions. Guidelines for management of infusion-related reactions are presented in [Table 12](#).

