## 9.6 Vital Signs

Vital signs (weight, systolic blood pressure, diastolic blood pressure) will be summarized with continuous descriptive statistics at Screening, on Cycle 1 Day 1 (assessed in 30-minute intervals), on all study treatment day 1 of each cycle, at EOT/Early Termination, and at Safety Follow up visit.

Vital Signs will be listed by patient and summarized by treatment and visit in the SAS.

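### SAP 9.3 appears to count infusion reactions by one preferred term, and SAP 9.6 tabulates no vital signs from the Day 8 and Day 15 infusions

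*SAP*

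**What the plan says.** TTI-621 is called PF-07901800 in the SAP. Protocol 3.8.1 reports that in TTI-621-01, the earlier weekly intravenous study, "the most frequent treatment-related adverse event was infusion-related reaction in 44% of patients".

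**Definition.** SAP 9.3 lists four adverse events of special interest. Thrombocytopenia and anemia use broad standardised queries and hemorrhage a narrow one. The fourth is "Infusion related reactions (PT of Infusion-related reaction as recorded on the Adverse Event CRF"). Item e of the planned tables begins "Summary of infusion related reactions (any grade and Grade", goes on to grade 3 or higher, and is to be split by system organ class and preferred term.

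**What a reaction looks like.** The note to Protocol Table 11 says "Signs/symptoms may include: allergic reaction/hypersensitivity (including drug fever); arthralgia" and goes on to name rigors or chills, hypotension, rash, tachycardia and others.

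**Vital signs.** SAP 9.6 states: "Vital signs (weight, systolic blood pressure, diastolic blood pressure) will be summarized with continuous descriptive statistics". The visits it names are Screening, Cycle 1 Day 1 (with 30-minute readings), Day 1 of each cycle, end of treatment and Safety Follow-up. Changes in vital signs are part of the primary safety endpoint for dose escalation (SAP 3.1) and of the secondary safety endpoint for the expansion cohorts (SAP 3.2).

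**The concern.** If one preferred term defines the event, a reaction counts only when the site enters it under that diagnosis. The same clinical episode entered as chills and fever is reported, but as two unrelated treatment-emergent events with no link to the infusion. The figure a reader will take as the infusion-reaction rate then depends partly on recording practice.

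Vital signs are the natural objective check, and the planned tables give little of it. Temperature, pulse and respiratory rate are among the measurements most relevant to an infusion reaction, and none is tabulated. Nor is any reading from the second infusion of a cycle. SAP 9.6 also mentions no change from a pre-infusion value, although the endpoint is worded as changes and Protocol 12.3.1 foresees change-from-baseline summaries where appropriate.

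**Working it through.** **1. The plan's own figures.** Protocol 3.5.2.1.2 and Table 1 report related events in TTI-621-01, with N = 235, starting with "infusion-related reaction (103 subjects, 44%), chills (49 subjects, 21"%). Dividing each count by 235:
- infusion-related reaction: 103/235 = 43.8% (stated 44%)
- chills: 49/235 = 20.9% (stated 21%)
- pyrexia: 26/235 = 11.1% (stated 11%)
- hypotension: 13/235 = 5.5% (stated 6%)

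All four reproduce. They also show that these symptoms were coded as separate related terms beside the infusion-reaction term.

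**2. How far a wider definition could move the rate.** The overlap between the four groups is not given, so only bounds are possible.
- Lower bound, every symptom patient also has the infusion-reaction term: 103/235 = 43.8%.
- Upper bound, no patient has two of the four terms: 103 + 49 + 26 + 13 = 191, and 191/235 = 81.3%. This is below the 193 patients with any related event, so that total does not rule it out.
- Difference: 191 − 103 = 88, so 0 to 88 patients, or 0 to 37.4 percentage points.
- Infusion-reaction term or chills only: 43.8% to (103 + 49)/235 = 64.7%.

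These ranges cover three symptom terms only; Table 11 lists more.

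**3. Is there a recording rule?** Protocol 13.5.8 requires events of special interest to be entered as an AE or SAE, and Table 11 grades a reaction as one entity. Neither says whether the symptoms go under that diagnosis or as separate entries. The instruction in Protocol 13.6 to group findings under a clinical syndrome covers laboratory abnormalities only.

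**4. Infusion days outside the vital-sign tables.** Cycles 1 to 6 have two TTI-621 infusions each (Day 1 and Day 8): 6 × 2 = 12, of which 6 are on Day 8. From Cycle 7 the infusions are on Day 1 and Day 15, so one of two per cycle is outside. Both come to half.

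**5. Collected against tabulated** (Protocol Table 24 notes a and c, and section 11; SAP 9.6).

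| Visit | Collected | Tabulated |
|---|---|---|
| Day 1 | temperature, systolic and diastolic pressure, pulse, respiratory rate, weight, oximetry | weight, systolic and diastolic pressure |
| Day 8, Day 15 | temperature, systolic and diastolic pressure, pulse, respiratory rate | none |

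That is 3 of 7 measurements on Day 1 and 0 of 5 on Day 8 and Day 15. Section 11 also requires a 60-minute observation with 30-minute readings after the Cycle 1 Day 8 infusion, and these readings enter no table.

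**The case against.** Little is actually lost from the report. Vital signs are listed by patient (SAP 9.6), and SAP 6.8 lists all recorded data by default. Chills, pyrexia and hypotension appear in the treatment-emergent tables by preferred term, and again in the treatment-related tables. Infusion interruptions are counted per drug (SAP 9.1), and events leading to interruption are tabulated (SAP 9.3). The continuous summaries in SAP 6.8 include the standard deviation, minimum, median and maximum as well as the mean. All of this stands. A reader might infer that Day 8 and Day 15 readings, or symptom-coded reactions, go unreported; they do not. What is missing is tabulation and a link to the infusion. Interruption counts do not fill that gap, because Table 12 allows a grade 1 reaction to be managed with the infusion continuing.

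The one-term reading is also not certain. Preferred terms are assigned in MedDRA coding, not recorded on a CRF, so the SAP may mean the preferred terms of events that the CRF identifies as infusion reactions. The split by preferred term in item e fits that better, since a single term would give a one-row table. The CRF is not among the documents, so this cannot be settled here; the SAP has to say which it means.

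The earlier rates may not carry over either. TTI-621-01 premedicated with an antihistamine and acetaminophen, and this trial adds a steroid to the prophylaxis (Protocol 3.8.1). Finally, the closing sentence of SAP 9.6 promises a summary by visit, which could be read generously as every visit. The preceding sentence names the variables and visits, however, and it is the one a programmer would follow.

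**Conclusion.** The point holds as a cheap improvement to the safety analysis.

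- **Infusion reactions.** SAP 9.3 appears to count them by a single preferred term, so symptom-coded reactions would be reported only as separate events. The bounds of 43.8% to 81.3% rest wholly on assumed overlap, and the upper one also treats every related chill, fever or fall in blood pressure as an infusion reaction. A reader might infer that the true rate is well above 44%, or that the single term is known to undercount. The documents support neither.
- **Vital signs.** The tables leave out half of the scheduled TTI-621 infusion days, and leave out temperature, pulse and respiratory rate at every visit. This follows directly from the visit schedule and needs no assumption beyond taking the list in SAP 9.6 at its word.

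A reader might also infer that recording habits will create a false dose difference. That is possible, because the cohorts did not all enrol over the same period, but nothing in the documents shows it. Cohorts A and B alternate while both are open (Protocol 7.2), and no test between doses is planned.

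**What to change.** **SAP 9.6.** Add temperature, pulse and respiratory rate, with oximetry for Day 1 visits only because it is not collected on Day 8 or Day 15. Include the Day 8 and Day 15 visits. For Cycle 1 Day 1 and Day 8, summarise each patient's worst post-infusion change from the same day's pre-infusion value. Keep later cycles descriptive: section 11 lists the post-infusion observation only for Cycle 1, and the synopsis lets investigators shorten it afterwards for patients without a reaction, so later readings would be missing selectively.

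**SAP 9.3.** State whether the event of special interest is the one preferred term or the events identified on the CRF, and keep that count. Add a supplementary count of patients with that term, or with a prespecified Table 11 symptom term judged related to PF-07901800 and starting on the infusion day or the next day. Leave out nausea, vomiting and fatigue, because emetogenic doxorubicin is given on the same Day 1. The two-day window is an assumption and should be labelled as one. Use only complete onset dates: SAP 6.5 moves onsets with a missing day in the month of first dosing to the first dose date, which would place them in the window artificially.

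**Cost.** SAP wording and programming from onset dates, causality by drug, infusion dates and vital signs already collected. The wider count will still pick up some doxorubicin or disease symptoms on Day 1, so it should stay supplementary. Day 8 and Day 15 infusions, given without doxorubicin, are less affected.
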